**Table RHBY.6.7. Description of Health Outcomes and Quality-of-Life Analyses**

Population	Variable	Analysis Method (Section 6.1)	Comparison/Time Point
RW ITT Population (to evaluate treatment effect in achieving/maintaining response during Period 2).	For other secondary objectives: Change from Baseline from originating study for: 
 
• Fatigue NRS score
 
• QID SR 16:               
 
Total score
 
• SF-36:                   
 
PCS
 
MCS
 
Associated domains
 
 
 
• ASAS HI
 
• EQ-5D-5L:                   
 
UK index; VAS
 
 
 
• WPAI-SpA:                   
 
% absenteeism; % presenteeism; % overall work impairment score; % activity impairment
 
 
 
• JSEQ
 
 
 
	Analysis of covariance (ANCOVA) with mBOCF	Total IXE vs. Placebo IXE80Q2W vs. Placebo IXE80Q4W vs. Placebo at each scheduled visit in Period 2 including Week 64.
Long-Term Ixekizumab Treatment Efficacy Population (to evaluate long-term treatment effect through Week 104 and Week 104)	For other secondary objectives: Change from baseline of the originating study for: 
 
• Fatigue NRS score
 
• QID SR 16:               
 
Total score
 
• SF-36:                   
 
PCS
 
MCS
 
 
 
 
 
	Descriptive statistics (for continuous variables using mBOCF and MMRM for data through Week 104)	IXE80Q2W a IXE80Q4W a Total IXE at each scheduled visit from Week 0 in originating study to Week 64 and Week 104, respectively.

Population	Variable	Analysis Method (Section 6.1)	Comparison/Time Point
respectively)	Associated domains • ASAS HI • EQ-5D-5L: UK index; VAS • WPAI-SpA: % absenteeism; % presenteeism; % overall work impairment score; % activity impairment • JSEQ		

Abbreviations: ASAS HI = ASAS Health Index ; EQ-5D-5L=European Quality of Life-5 Dimensions-5 Level; ITT = intent-to-treat; IXE80Q2W = ixekizumab 80 mg every 2 weeks; IXE80Q4W = ixekizumab 80 mg every 4 weeks; JSEQ = Jenkins Sleep Evaluation Questionnaire ; mBOCF = modified baseline observation carried forward ; MCS = mental component summary; MMRM = mixed model for repeated measures; NRS = numeric rating scale; PCS = physical component summary; QIDS SR 16=Quick Inventory of Depressive Symptomatology-Self Report 16 items; SF-36 = Medical Outcomes Study 36-Item Short-Form Health Survey.

a IXEQ2W is a group of patients who have been treated consistently with ixekizumab 80 mg every 2 weeks since Week 0 in the originating studies through Week 64 of RHBY. IXEQ4W is a group of patients who have been treated consistently with ixekizumab 80 mg every 4 weeks since Week 0 in the originating studies through Week 64 of RHBY.

## 6.12. Bioanalytical and Pharmacokinetic/Pharmacodynamic Methods

Observed ixekizumab serum concentrations will be summarized by treatment group, visits, and corresponding time when sampling occurred. The potential impact of immunogenicity on ixekizumab concentrations may be evaluated by graphical assessments, as appropriate, to compare drug concentration levels between anti-drug antibody (ADA) negative and ADA positive patients at corresponding visits, or before and after ADA development for patients who developed ADA. A similar approach may be taken if patients become NAb positive.

Additional exploratory analyses including the PK data may be conducted if deemed appropriate.

## 6.13. Safety Analyses

Safety will be assessed by summarizing and analyzing AEs, laboratory analytes, vital signs, QIDS-SR16, and the Columbia Suicide Severity Rating Scale (C-SSRS). The duration of treatment exposure will also be summarized.

For Period 2, safety data will be summarized for the RW Safety Population. Treatment group comparisons will be performed on categorical safety data using Fisher's exact test, and continuous safety data will be analyzed by an ANCOVA model as described in Section [6.1.3](#).

For Combined Periods 1 and 2 (Lead-In Period Safety Population), Combined Periods 1, 2, and 3 (Lead-In Period Safety Population), Period 2 (RW Safety Population), and Period 4 (Follow-Up Period Population), the above safety variables will be summarized as described in Sections [6.1.3](#), [6.1.4](#), and [6.1.6](#), respectively.

For safety analyses, unless otherwise specified, the following baselines will be used:

- Treatment-emergent adverse events for RW Safety Population during Period 2:
  - The baseline is events ongoing prior to the first injection in Period 2.
- Treatment-emergent adverse events for Lead-In Period Safety Population during Combined Periods 1 and 2, and Combined Periods 1, 2, and 3:
  - For patients who were not randomized to placebo at Week 24, the baseline is the events ongoing prior to the first injection in Period 1;
  - For patients who are randomized to placebo at Week 24 and then are retreated with ixekizumab, the baseline for TEAEs during Period 1 is the events ongoing just prior to the first injection in Period 1, but the baseline for TEAEs after retreatment of ixekizumab is the events ongoing just prior to the first injection of retreatment during Periods 2 and 3 Combined.
- Change from baseline to minimum/maximum postbaseline, to last observation and to each scheduled postbaseline visit for laboratory and vital signs, and for treatment-emergent abnormal laboratory and vitals, including shift tables (hepatic or cytopenia labs) and the elevation of hepatic labs:
  - For Lead-In Period Safety Population during Combined Periods 1 and 2, and Combined Periods 1, 2, and 3, the baseline is the last nonmissing value prior to the first injection in Period 1 regardless of changes of treatment regimen;

- For RW Safety Population during Period 2, the baseline is the last nonmissing value prior to the first injection in Period 2.

### 6.13.1. Extent of Exposure

Duration of exposure to study drug will be summarized by treatment group for RW Safety population for Period 2 and Lead-In Period Safety Population for Combined Periods 1 and 2 and Combined Periods 1, 2, and 3 using descriptive statistics.

- The duration of exposure for RW Safety Population during Period 2 will be calculated as:

*Duration of exposure (days)*

$$= \text{Date of last visit (scheduled or unscheduled) in Period 2} \\ - \text{Date of first dose in Period 2} + 1$$

- The duration of exposure on ixekizumab for Lead-In Period Safety Population during Combined Periods 1 and 2 or Combined Periods 1, 2, and 3:

- For patients on uninterrupted ixekizumab treatment regimen during Combined Periods, it will be calculated as:

*Duration of exposure (days)*

$$= \text{Date of last visit (scheduled or unscheduled) in the Combined Periods} \\ - \text{Date of first dose in Periods 1} + 1$$

- For patients who are randomized to placebo at Week 24, ixekizumab exposure will be calculated as:

$$\text{Duration of exposure (days)} = \text{Duration 1} + \text{Duration 2},$$

where duration 1 = *Date of last visit in Period 1 – Date of first dose in Period 1* + 1 and duration 2 =

*Date of last visit on retreatment on ixekizumab in the combined periods – Date of first dose of retreatment on ixekizumab in the combined periods* + 1,

where duration 2 is a non-zero value for patients who are retreated with ixekizumab during the combined periods, and it is 0 for patients who are on placebo from Week 24 to the end of the combined periods.

The number and percentage of patients in each of the following categories will be included in the summaries:

#### For Period 2:

- >0,  $\geq 28$  days,  $\geq 56$  days,  $\geq 84$  days,  $\geq 120$  days,  $\geq 183$  days. Note that patients may be included in more than 1 category.
- >0 to <28 days,  $\geq 28$  to <56 days,  $\geq 56$  to <84 days,  $\geq 84$  to <120 days,  $\geq 120$  to <183 days, and  $\geq 183$  days.

**For combined Periods 1 and 2:**

- $>0, \geq 28 \text{ days}, \geq 56 \text{ days}, \geq 84 \text{ days}, \geq 120 \text{ days}, \geq 183 \text{ days}, \text{ and } \geq 365 \text{ days}$ . Note that patients may be included in more than 1 category.
- $>0 \text{ to } <28 \text{ days}, \geq 28 \text{ to } <56 \text{ days}, \geq 56 \text{ to } <84 \text{ days}, \geq 84 \text{ to } <120, \geq 120 \text{ to } <183 \text{ days}, \geq 183 \text{ to } <365 \text{ days}, \text{ and } \geq 365 \text{ days}$ .

**For combined Periods 1, 2 and 3:**

- $>0, \geq 28 \text{ days}, \geq 56 \text{ days}, \geq 84 \text{ days}, \geq 120 \text{ days}, \geq 183 \text{ days}, \geq 365 \text{ days}, \geq 548 \text{ days}$ . Note that patients may be included in more than 1 category.
- $>0 \text{ to } <28 \text{ days}, \geq 28 \text{ to } <56 \text{ days}, \geq 56 \text{ to } <84 \text{ days}, \geq 84 \text{ to } <120, \geq 120 \text{ to } <183 \text{ days}, \geq 183 \text{ to } <365 \text{ days}, \geq 365 \text{ to } <548 \text{ days}, \text{ and } \geq 548 \text{ days}$ .

The summaries will also include the following information:

- Total exposure in patient years, calculated as:

$$\text{Total exposure in patient years} \\ = \frac{\text{Sum of duration of exposures for all patients in treatment group}}{365.25}$$

- Mean and median total dose for each treatment group. Total dose (in mg) is calculated by the number of active injections taken during the treatment period multiplied by dose. The total dose (in mg) taken during Combined Periods 1, 2, and 3 and Periods 2 will be calculated as follows:

*Total dose for a patient on ixekizumab 80 mg Q2W or Q4W in a specific period*  
 $= \text{Total number of active injections received in that period} \times 80$

- Total number of injections received will be derived using the response to the question “Was dose administered?” on the *Exposure as Collected* eCRF page and the actual dose description from IWRS study drug dispense dataset.

### 6.13.2. Adverse Events

Adverse events (AEs) will be classified based upon the latest version of the MedDRA. Adverse events will be recorded at every study visit. Any condition starting on or after the date of informed consent will be considered an AE. Any preexisting condition which worsens in severity on or after the date of informed consent will be considered and recorded as an AE on the *Adverse Event (AE)* eCRF page from the date of worsening onwards.

A treatment-emergent adverse event (TEAE) is defined as an event that first occurred or worsened in severity after baseline and on or prior to the date of the last visit within the defined treatment period. Both the date/time of the event and the date/time of the dose (that is, injection) are considered when determining TEAEs. Treatment-emergent AEs will be assigned to the study period to which it's considered treatment-emergent:

- The MedDRA lowest level term (LLT) will be used when classifying AEs as treatment-emergent.
- The maximum severity recorded for each LLT prior to the first dose date/time in the treatment Period will be used as the pre-treatment severity for that LLT. If an event during the baseline period has missing severity, and the event persists during the treatment period, then it will be considered as treatment-emergent, regardless of the postbaseline level of severity. Events with a missing severity during the treatment period will be considered as treatment-emergent.
- AEs with a particular LLT will be classified as treatment-emergent if they first start on or after the first dose date/time in the treatment period (ie, a patient has no preexisting conditions with that lowest level term), or if the severity is greater than the pre-treatment severity for that lowest level term. If a partial AE start date/time is present, the date/time will be compared as far as possible to the treatment start date/time in order to determine whether the event is treatment-emergent or not. If there is any doubt, the event will be flagged as treatment-emergent.

A follow-up emergent adverse event (FEAE) is defined as an event that first occurred or worsened in severity after the date of Visit 14 (Group A) or Visit 519 (Group B) (that is, Week 104) or the ETV:

- The MedDRA LLT will be used when classifying AEs as follow-up emergent.
- For AEs that are ongoing at the date of Visit in Week 104 or ETV, the maximum severity recorded for each LLT on or prior to the date of the Visit at Week 104 or ETV will be used as the follow-up baseline severity for that LLT.

If a partial or completely missing AE start date/time or end date/time is present, the following imputation rules will be utilized in the analysis:

- For the start date:
  - If year, month, and day are missing, then use the earlier of the patient's first visit date or the consent date.
  - If either month or month and day are missing, then use January 1.
  - If only day is missing, impute the first day of the month.
- For the start time:
  - Impose as 23:59
- For the end date:
  - If year, month, and day are missing, then use the patient's last visit date in the follow-up period.
  - If either month or month and day are missing, then use December 31.
  - If only day is missing, then use the last day of the month.
  - The imputed date will not be beyond the patient's last visit date in the follow-up period.
- For the end time:
  - Impose as 23:59.

- If there is any doubt, the event will be flagged as treatment-emergent or follow-up emergent according to the corresponding study period. If a follow-up emergent event is already counted as treatment-emergent during the prior treatment period, it will not be counted as a follow-up emergent event.

Adverse events and TEAEs will be summarized for the following study periods by treatment groups (see [Table RHBY.6.1](#)) and analysis populations, treatment comparisons between treatment groups in Period 2 will be conducted using a Fisher's exact test:

- Combined Periods 1 and 2, Combined Periods 1, 2, and 3 (Lead-In Period Safety Population)
- Period 2 (RW Safety Population).

The following summaries/analyses will be performed:

- An overall summary of AEs including the number and percentage of patients who experienced TEAE, TEAE by maximum severity, death, SAE, TEAE possibly related to study treatment occurring in  $\geq 5\%$  of patients in the total ixekizumab group, SAE judged by investigator as possibly study treatment related (for combined periods only), discontinuations from the treatment due to an AE, and TEAEs of special interest.
- TEAE by SOC and PT.
- TEAE by maximum severity, SOC, and PT.

The overall summary of AEs will also be provided for the RW Safety Population during Period 3, Long-Term Ixekizumab Treatment Efficacy Population and Ixekizumab Structure Population by treatment groups.

Follow-up emergent adverse events will be summarized for the Follow-Up Period Population for Period 4:

- FEAEE by PT.

In general, for all AE-related summaries, the number and percentage of patients experiencing the events will be presented by treatment group. In general, events will be ordered by decreasing frequency in the Combined Ixekizumab group, followed in the order of ixekizumab Q2W, ixekizumab Q4W, and placebo (when applicable) group, within SOC and/or PT for sorting.

A by-patient listing of all AEs will be provided.

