### **6.1.2. General Considerations for Analyses during the Combined Periods 1, 2, and 3**

Combined Periods 1 and 2 starts at the first injection of IXE80Q2W or IXE80Q4W in RHYB, and ends on the injection date of Week 64 (Group A: Visit 10/Group B: Visit 515) or next injection date after Week 64 if injection date of Week 64 is missing which is the start date of Period 3, or at ETV prior to Week 64.

Combined Periods 1, 2, and 3 starts at the first injection of IXE80Q2W or IXE80Q4W in RHYB, and ends on the date of Week 104 visit (Group A: Visit 14/Group B: Visit 519) or at ETV prior to Week 104.

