### ***6.1.3. General Considerations for Analyses during the Extension Period Including the Double-Blind RW Period (Period 2)***

#### **6.1.3.1. RW ITT and RW Safety Populations**

For patients who are randomized in Period 2 (group B), comparisons between Combined Ixekizumab treatment group and placebo, as well as between each ixekizumab regimen (80 mg Q2W or 80 mg Q4W) and placebo, will be performed for all analyses at each scheduled visit in Period 2 including Visit 515 at Week 64.

Period 2 starts at the first injection of study treatment after randomization (at Week 24) and ends at the following study events:

- Prior to the first injection of study treatment at Week 64 (Visit 515) for not retreated patients who have completed visit at Week 64. If injection at Week 64 is missing, the next injection date after Week 64 is used;
- Prior to the first injection of retreatment for patients who have been retreated within Period 2;
- ETV prior to Week 64.

For patients who are in the RW ITT Population and have been retreated with the ixekizumab treatment regimen due to a flare or any other reasons, only data prior to the time of the retreatment will be included in the analysis for Period 2. Data after retreatment will be imputed using nonresponder imputation (NRI) method for categorical variables and mBOCF method for continuous variables.

The observed values after retreatment will be used for other specified analysis, for example, efficacy analysis for Flare Population with Retreatment.

For efficacy and health outcomes, baseline is defined as the last available value before the first dose of study treatment in Period 2 from the originating study and, in most cases, will be the value recorded at Week 0 from the originating study.

The primary analysis method for treatment comparisons of categorical binary efficacy and health outcome variables will be a logistic regression with treatment group, geographic region, and originating study as factors using PROC Logistic with Wald method. The odds ratio and 95% CIs will be reported; treatment difference and 95% CI will also be reported. In the case when logistic regression model does not produce statistical results due to sparse data, Fisher's exact test will be used. Same analysis will also be carried out at each of other scheduled visits in Period 2.

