### **6.1.6. General Considerations for Analyses during the Post-Treatment Follow-Up Period (Period 4)**

Period 4 starts at the date of the visit (Group A: Visit 14/Group B: Visit 519) at Week 104 or at ETV and ends at study completion or at the last visit prior to study discontinuation. Safety data collected during Period 4 will be summarized by treatment that the patients are taking prior to entering Period 4.

For the safety analyses during Period 4, baseline is defined as the last nonmissing assessment prior to entering Period 4, that is, on or prior to Week 104 (Group A: Visit 14/Group B: Visit 519), or ETV.

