#### **6.13.3.1. Special Safety Topics including Adverse Events of Special Interest**

Safety information on special topics including AEs of special interest (AESI) will be presented by treatment group and by analysis period.

Table [RHBY.6.8](#) provides the definitions/derivations and analyses methods (including analyses, summaries and by-patient listings) of special safety topics including AESIs.

Potential AESIs will be identified by a standardized MedDRA query (SMQ) or a Lilly-defined MedDRA PT listing. Preferred terms within an SMQ will be classified as broad and narrow. In the Lilly-defined MedDRA PT listings, Lilly has provided the broad and narrow classification. The Lilly-defined broad terms are for a more sensitive search of potential events of interest and the Lilly-defined narrow terms are for a more specific search. Therefore, the summaries will include the classifications of broad term (same as pooling narrow and broad terms together) and narrow term.

Summaries will be provided for the Lead-In Period Safety Population in the Combined Periods 1 and 2, and Combined Periods 1, 2, and 3, and for RW Safety Population in Period 2. Fisher's exact tests will be used to compare the treatment group for the RW Safety Population during Period 2.

In general, an AESI summary will not be provided for the Follow-Up Period Population during Period 4 except for hepatic laboratory tests.

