Major Adverse Cerebro-Cardiovascular Events (MACE)	
MACE (requiring adjudication as defined above) is defined as:
 
 
● Vascular Death (including cardiovascular and cerebro-vascular causes excluding hemorrhagic deaths outside of the central nervous system)
 
● Non-fatal myocardial infarction
 
● Non-fatal stroke (subtypes: hemorrhagic stroke, ischemic stroke, undetermined stroke type)
 
 
Where,
 
 
● Vascular death should be captured as an Event on Adjudication - Death eCRF page with Adjudication Death Type = "Cardiovascular."
 
● Non-fatal myocardial infarction should be captured as an Event on Adjudication - Cardiac Ischemic Event eCRF page with Type of Ischemic Event = "Myocardial Infarction" and the Event is NOT on
 
	
Period 2 (Fisher's exact test), Combined Periods 1 and 2, Combined Periods 1, 2, and 3 (Summary): TEAE by maximum severity by PT within category
 
Listing (in Spotfire): TEAE

Special Safety Topic	Definition / Derivation	Analysis / Summary / Listing
	
Adjudication - Death eCRF page.
 
 
Non-fatal strokes (ischemic, hemorrhagic) should be captured as an Event on Adjudication - Cerebrovascular Event eCRF page with Stroke Cerebrovascular Event Subtype in 1 of the following categories: hemorrhagic stroke, ischemic stroke, undetermined stroke type, and the Event is NOT on Adjudication - Death eCRF page. Subcategories of non-fatal stroke (Hemorrhagic Stroke, Ischemic Stroke, and Undetermined Stroke Type) will be displayed nested within non-fatal stroke category.
 
	

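### An event starting after the last visit, in a patient with no Week 104 visit or ETV, is neither treatment-emergent nor follow-up emergent under SAP 6.13.2

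*SAP*

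**What the plan says.** SAP 6.13.2 defines a TEAE as an event that first occurs or worsens "after baseline and on or prior to the date of the last visit within the defined treatment period". A follow-up emergent event must occur or worsen "after the date of Visit 14 (Group A) or Visit 519 (Group B) (that is, Week 104) or the ETV".

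The period definitions hang on the same two visits. Under SAP 6.1.2 the Combined Periods 1, 2 and 3 window "ends on the date of Week 104 visit (Group A: Visit 14/Group B: Visit 519) or at ETV prior to Week 104". Under SAP 6.1.6, "Period 4 starts at the date of the visit (Group A: Visit 14/Group B: Visit 519) at Week 104 or at ETV". Follow-up emergent events are summarised only for the Follow-Up Period Population, whose members must have entered Period 4 (SAP 6.1.1 and 6.13.2).

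In SAP Table RHBY.6.8 the planned MACE summary is "TEAE by maximum severity by PT within category", and vascular death is a MACE component. The cerebro-cardiovascular row and the Depression row (an SMQ that includes suicide/self-injury) also specify TEAE summaries and TEAE listings. The text of the cerebro-cardiovascular row nevertheless says that all events qualifying for adjudication by the events committee enter that analysis.

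Protocol Appendix 1 defines a TEAE as occurring or worsening at any time after treatment baseline, with no upper limit.

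**The concern.** The two classes are meant to cover all on-study time after first dose: treatment-emergent up to the closing visit, follow-up emergent after it. They do so only for a patient who has a closing visit. A patient who dies between visits does not have one, and neither does a patient who stops attending and refuses an ETV. For them, the time after the last visit belongs to no class.

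The events most exposed to this gap are sudden deaths, and several of the special-interest outputs exist to count exactly those. SAP 6.13.2 reports adverse events as number and percentage of patients, so the patient stays in the denominator while the event leaves the numerator. These are rare outcomes, for which a single case is informative.

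**Working it through.** The plan states no figure on this point, so there is nothing to reproduce. The check applies the SAP date rules to a dated event.

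**Worked case.** A patient attends Week 76, has a sudden fatal myocardial infarction at Week 84, and would next have been seen at Week 88.
- TEAE: onset (Week 84) is after the last visit (Week 76), so no.
- Follow-up emergent: there is no Week 104 visit and no ETV, so no.
- Period 4: never entered, so the patient is not in the Follow-Up Period Population.
- MACE table, as specified: 0 events. Overall death count: 1. SAEs by preferred term: 1.

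**How general this is.** Take a sudden fatal event, with onset on the day of death, on each of days 1 to 727. Let the last visit be the latest scheduled visit on or before that day, with no ETV. The event is a TEAE only if it falls on a visit day. From the protocol's Schedule of Activities:
- Group A has visits after Week 0 and before Week 104 at Weeks 8, 16, 20, 24, 32, 40, 48, 56, 64, 76, 88 and 100: 12 days. In neither class: 727 − 12 = 715 days, and 715/727 = 98%.
- Group B adds Weeks 28, 36, 44, 52 and 60: 17 days. In neither class: 727 − 17 = 710 days, and 710/727 = 98%.

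These percentages describe how the rule treats a sudden death with no closing visit. They say nothing about how many such deaths will occur.

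**Length of the uncovered interval.** Visit gaps are 4 or 8 weeks up to Week 64, 12 weeks from Week 64 to Week 100, and then 4 weeks. If deaths are uniform over the 728 days (an assumption), the mean time from last visit to event is Σ(gap in days)²/(2 × 728).
- Group A: seven gaps of 8 weeks, three of 4 and three of 12. The squared weeks sum to 448 + 48 + 432 = 928, and 928 × 49/1,456 = 31 days.
- Group B: two gaps of 8 weeks, thirteen of 4 and three of 12. The sum is 128 + 208 + 432 = 768, and 768 × 49/1,456 = 26 days.

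**Does another rule close the gap?** The instruction in 6.13.2 to flag doubtful events as emergent accompanies the rules for partial or missing dates. A death with a known date raises no such doubt. One operational bullet in 6.13.2 gives a start (first dose) and no end, which is wider than the main definition but does not override it. No text extends the window to death, to last contact or to an interval after the last dose.

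**The case against.** The strongest reply is that these events are reported elsewhere, and that stands. SAP 6.13.2 puts deaths and SAEs in the overall summary by treatment group. SAP 6.13.3 lists all deaths and tabulates SAEs, and adverse events leading to discontinuation (including death), without limiting them to TEAEs. SAP 6.19 counts SAEs for the registry whether or not they are treatment-emergent. A reader might infer that fatal events disappear from the report, or that the overall safety conclusion is biased low. The documents support neither.

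Other parts of the reply also stand:
- The affected group is narrow. The protocol asks patients who stop treatment to complete an ETV, and an event before a later ETV is inside the window. An event that began on or before the last visit stays a TEAE even if death follows.
- The SAP says last visit, not last attended visit. Whether a death generates a closing visit record depends on form conventions that the documents do not show.
- The sentence on adjudicated events makes the cerebro-cardiovascular row internally inconsistent rather than plainly TEAE-only.
- The suicide effect is confined to the Depression and suicide/self-injury SMQ outputs. The C-SSRS and self-harm data are listed, not tabulated (SAP 6.13.7).

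Two neighbouring points might be drawn in and should not be. SAP 6.13.3.1 omits most Period 4 special-interest summaries, but that is a stated scope choice, and follow-up events are still summarised by preferred term. SAP 6.1.3.1 ends Period 2 just before the next injection rather than at the last visit. That gap is normally short, since protocol 7.4 starts Period 2 retreatment at a scheduled visit.

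What the reply does not answer is that none of the surviving outputs is the MACE count or the suicide/self-injury count.

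**Conclusion.** The point holds in a limited form. For a patient with neither a Week 104 visit nor an ETV, an event starting after the last visit is neither a TEAE nor follow-up emergent. As written, it is missing from the TEAE tables and from the MACE, cerebro-cardiovascular and Depression and suicide/self-injury SMQ outputs. This is more than missing detail: a stated rule gives a wrong count, departs from the protocol's open-ended definition, and conflicts with the SAP's own sentence on adjudicated events.

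The number affected is likely small. A reader might multiply total exposure by a background death rate to size it. The documents give no such rate, and the result would be all deaths, not those that start after the last visit without an ETV. What can be said is that one omission changes a count of 1 to 0, and that one report could show a vascular death in its death count and no MACE. The conclusion assumes the main definition in 6.13.2 is programmed literally and that a death does not itself create an ETV record.

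**What to change.** In SAP 6.13.2, add that for a patient with no Week 104 visit or ETV the TEAE window ends at the date of death or of last contact. If a cap after the last dose is wanted, state it as an analysis choice. It should not be described as the protocol's minimum follow-up, because those 12 weeks run from the last regularly scheduled visit or the ETV, not from the last dose.

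Use the same end date for exposure in SAP 6.13.1, which now stops at the last visit. In Table RHBY.6.8, state that adjudicated deaths are counted in the MACE and cerebro-cardiovascular tables under their adjudicated category, whatever their TEAE status.

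The cost is a few sentences and a small programming change, with no new data. Exposure rises slightly for a few patients: about 31 days (Group A) or 26 days (Group B) on average for each such death, under the uniform-timing assumption and with no cap.
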